made meal services (Pangea Keto, Factor, Fresh and Lean). After the initial 2 weeks, and until completion of the 8-week intervention, the participants will not be supplied with all their food but will continue to receive educational materials, recipe guides and dietitian consultation as needed. Participants will have 24-hour access to the dietetic team to answer questions. After the initial 2 weeks, participants will switch to a self-guided dietary approach. Adherence will be prospectively evaluated throughout the study period. Subjects will be asked to use the meter each morning and to submit the results to the research team through a secure KetoMojo provider/consumer sharing application. Results will be recorded by a member of the research team. Levels of ketosis and glucose will be monitored daily. Participants will be asked to maintain levels of ketones that are equal or greater than 0.5mmol/L.

DATA ANALYSIS AND STATISTICAL METHODS

Statistical Plan: To evaluate the impact of the ketogenic diet intervention on menstrual cycle regularity in women with PCOS, we have the following data analysis plan:

- 1) Descriptive Analysis: We will provide concise summaries of menstrual cycle attributes such as cycle length, variability, and ovulation status for participants at baseline.
- 2) Menstrual Cycle Regularity Assessment: Survival analysis techniques, including Kaplan-Meier curves and log-rank tests, will be employed to compare the timeframe required to establish regular menstrual cycles (21-35 days range). Observations censored due to drop-outs or non-occurrences of events will be appropriately handled.
- 3) Ovulation Pattern Analysis: We will utilize logistic regression analysis to assess the effect of the ketogenic diet on the incidence of ovulation in PCOS women, considering each cycle as an independent statistical unit. This analysis will offer quantifiable insights into the probability of ovulation in the study population, considering potential confounders like age, BMI, and initial menstrual cycle characteristics.
- 4) Effect Size Estimation: Hazard ratios and their confidence intervals will be calculated to quantify the influence of the ketogenic diet on attaining regular menstrual cycles.

5) Significance Testing: The proportion of participants achieving regular menstrual cycles in each diet group will be compared using appropriate statistical tests such as the chi-square test.

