Through this robust analytical strategy, we aim to unravel the influence of a ketogenic dietary intervention on menstrual cycle regularity and ovulation patterns in women with PCOS, thereby providing a compelling narrative around the potential benefits of a ketogenic diet.

STUDY MONITORING

Concomitant Medication/Supplements and Treatment

All concomitant medications/supplements used 1 months prior to Screening Visit and during the study will be reported to the study personnel for assessment and recorded in the participant's study documents.

Radiation

This study comprises two, whole-body DXA scans, eight-weeks apart. This radiation exposure is not necessary for medical care and is for research purposes only. The total amount of radiation is about 78 mrem and is approximately equivalent 95 days of exposure to natural background radiation. This procedure involves minimal risk and is necessary to obtain the research information about changes in lean body mass, fat mass, and bone density (i.e., 3-compartment assessment model).

Adverse Event Monitoring

An AE is defined as any untoward medical occurrence in an investigation participant following written informed consent that does not necessarily have a causal relationship with the study product. An AE can be any unfavorable or unintended sign (including an abnormal finding), symptom, or disease temporally associated with the use of an investigational product, whether or not related to the investigational product. This includes any occurrence that is new in onset or aggravated in severity or frequency from the baseline condition, or abnormal results of diagnostic procedures (including laboratory test abnormalities).

Some side effects or GI symptoms could occur as an outcome of these dietary interventions; side effects listed in the beverage tolerability questions and reported will not be categorized as AEs but recorded as study outcomes. Side effects, outside of what is expected as a result of study product consumption, reported by participants and judged by the Investigators as medically relevant events and related to study product will be recorded as AEs.

Events should be considered AEs if they:

- Result in discontinuation from the study,
- Require treatment or any other therapeutic intervention,
- Require further diagnostic evaluation (excluding a repetition of the same procedure to confirm the abnormality),

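### The only primary outcome is change in anovulatory status, but the participant-level test and the hazard ratio are on menstrual regularity, and the one ovulation analysis treats cycles as independent

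*Protocol*

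**What the plan says.** The Study Synopsis, the Outcomes section and the outcome table repeated within Diet Intervention all name one primary outcome, change in anovulatory status. The secondary outcomes are reproductive hormones, predictive baseline characteristics and blood metabolites; the exploratory outcomes are from MRI. Menstrual regularity is in none of the lists. The Sample Size paragraph ties the 40 women, 20 per arm, to effects on ovulation.

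The Statistical Plan, under Data Analysis and Statistical Methods, states its purpose as "To evaluate the impact of the ketogenic diet intervention on menstrual cycle regularity in women with PCOS". Its items are:

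- Item 1 is descriptive. It includes "ovulation status for participants at baseline".
- Item 2 compares time to regular cycles of 21 to 35 days by Kaplan-Meier curves and log-rank tests.
- Item 3 uses logistic regression to "assess the effect of the ketogenic diet on the incidence of ovulation in PCOS women, considering each cycle as an independent statistical unit". It adjusts by "considering potential confounders like age, BMI, and initial menstrual cycle characteristics".
- Item 4 is the estimate that goes with item 2: "Hazard ratios and their confidence intervals will be calculated to quantify the influence of the ketogenic diet on attaining regular menstrual cycles".
- Item 5, on significance testing, reads: "The proportion of participants achieving regular menstrual cycles in each diet group will be compared using appropriate statistical tests such as the chi-square test".

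The closing paragraph widens the aim to "menstrual cycle regularity and ovulation patterns in women with PCOS" but adds no method.

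**The concern.** Two things are wrong as written. First, the participant-level test, the time-to-event test and the hazard ratio all address an outcome that the protocol does not list. The background section on ketogenic interventions in PCOS says that having periods is not proof of ovulating, and presents unproven ovulation as the gap left by earlier studies. Those regularity analyses can come out either way without answering the question for which the women are recruited.

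Second, the only between-arm analysis of ovulation counts repeated cycles of one woman as separate evidence. If cycles within a woman are alike, its standard errors are too small. It also gives more weight to women who complete more cycles, and the number of cycles may itself respond to the diet.

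The Impact section says the pilot is to inform a later fully powered trial. A mis-targeted or over-precise ovulation estimate would carry into that design.

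**Working it through.** **Outcome against analysis.** The protocol gives no alpha, power, effect size or event count, so it has no figure of its own to reproduce. The between-arm analyses count as follows.

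| Endpoint | Items | Listed as an outcome? |
|---|---|---|
| Time to regular cycles | 2 (test), 4 (estimate) | No |
| Proportion of women who become regular | 5 | No |
| Ovulation per cycle | 3 | Yes, the only primary |

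**Cycles per woman.** The synopsis gives 12 weeks, or 84 days. Two complete cycles then need a cycle length of 84/2 = 42 days or less. Diet Intervention speaks of an 8-week intervention, or 56 days, which needs 56/2 = 28 days or less. Both limits assume that a cycle starts on the first day of follow-up. The inclusion criteria cover oligomenorrhea, so some women may complete only one cycle.

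**Effect of assuming independence.** Let m be the cycles per woman and rho the within-woman correlation (assumed; the protocol gives none). The design effect is DE = 1 + (Σm²/Σm − 1) × rho. The true two-sided error of a nominal 5% test is 2 × (1 − Φ(1.96/√DE)).

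| Cycles per woman | rho | DE | True error | Simulation |
|---|---|---|---|---|
| 1 | any | 1.0 | 5.0% | not run |
| half 1, half 2 | 0.3 | 1 + (5/3 − 1) × 0.3 = 1.2 | 7.4% | 7.2% |
| 2 | 0.1 | 1.1 | 6.2% | 6.0% |
| 2 | 0.3 | 1.3 | 8.6% | 8.4% |
| 2 | 0.5 | 1.5 | 11.0% | 10.9% |

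The simulation was beta-binomial: 200,000 runs, 20 women per arm, 30% of cycles ovulatory, unadjusted chi-square on pooled cycles. With three cycles per woman the formula gives 12.1% at rho 0.3. At two cycles and rho 0.3, a correct interval is √1.3 = 1.14 times as wide, or 14% wider.

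**Regularity in place of ovulation (illustration on assumed rates).** Suppose ovulation is 50% against 20%, every ovulating woman is regular, and a fraction q of the others is regular in both arms. Then regular = ov + (1 − ov) × q.

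- q = 0.2: 0.50 + 0.50 × 0.2 = 60% against 0.20 + 0.80 × 0.2 = 36%, a difference of 24 points.
- q = 0.4: 0.50 + 0.50 × 0.4 = 70% against 0.20 + 0.80 × 0.4 = 52%, a difference of 18 points.

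The 30-point ovulation difference is diluted in both cases.

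**What a participant-level ovulation comparison would give.** For 10/20 against 4/20 the Wilson limits are 29.9% to 70.1% and 8.1% to 41.6%. The Newcombe interval for the 30-point difference runs from 30 − √(20.1² + 21.6²) = 0.5 to 30 + √(20.1² + 11.9²) = 53.4 points. Power for true rates of 50% and 20% is about 51% at an assumed two-sided 5% level.

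**The case against.** The strongest reply is that ovulation does have an analysis. Item 3 compares it between diets with adjustment, the closing paragraph names ovulation patterns alongside regularity, and nothing in the plan calls regularity primary or uses it to estimate ovulation. That is fair. The fault is that an unlisted outcome holds the participant-level and time-to-event tests, while the listed one has only an analysis with the wrong unit. The dilution figures show what would happen if regularity were read as ovulation; they do not measure a loss in the plan as written.

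The inflation may also be small. With oligomenorrhea, or with the 8-week duration, many women may have a single cycle, and then there is none. The baseline covariates in item 3 may absorb part of the between-woman variation, so the relevant correlation is the residual one and may be below 0.3; the error rates above come from an unadjusted test. These points bear on the size. Covariates do not model the clustering, and any positive residual correlation with more than one cycle works in the same direction.

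The trial is a pilot that admits limited power, so interval width matters more than nominal test error. That stands, but the interval is what the later trial would use. Nor is this detail left to a statistical analysis plan: the protocol itself states the independence of cycles, and a later plan would have to contradict it.

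**Conclusion.** The concern holds and should be fixed. The mismatch between the primary outcome and the analyses is plain from the text and rests on no assumption, and so is the statement that cycles are independent. The direction of the error in item 3 is certain once women contribute more than one positively correlated cycle.

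Its size is not known. It ranges from none at one cycle per woman to a true error of about 6% to 11% at two cycles, with correlations of 0.1 to 0.5, and more with further cycles. Correlation, cycle counts and ovulation rates are assumptions, and covariate adjustment could lower the figures.

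**What to change.** 1. Name as the primary analysis a participant-level comparison between arms of confirmed ovulation during the intervention, with an effect estimate and 95% interval, in all randomised women. An adjusted logistic model should replace the chi-square test here, because chi-square cannot adjust. Adjust for baseline ovulation status where it is available; item 1 plans to summarise it, and the initial cycle characteristics in item 3 may already cover it.
2. In item 3, delete the statement that cycles are independent and account for clustering by woman, for example with GEE or a random effect. This corrects the interval. It does not by itself remove the extra weight on women with more cycles, which is why the participant-level analysis should lead.
3. Add menstrual regularity to the secondary outcomes, label items 2, 4 and 5 as supportive, and reword the opening purpose to put ovulation first.
4. Reconcile the 8-week and 12-week durations, since they set how many cycles a woman can contribute.

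The cost is text only. The ovulation rule can use the temperature, progesterone and LH-strip data already planned. Two limits remain. The blood schedule is in Figure 2, which could not be seen, so whether progesterone timing suffices is unchecked. The visible text describes no tracking before the diet, so baseline ovulation status may be missing for some women. Regularity loses its headline place, the item 3 interval widens (about 14% at two cycles and correlation 0.3), and the participant-level interval will be wide.

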As the hormone dynamics could shift when an individual is on a ketogenic intervention, testing will be moved to biweekly to capture these changes. These changes are already in effect in the SPARK001 participant in the study.

IMPACT

Our intent is to produce preliminary feasibility and efficacy data to inform the design of a future fully-powered, clinical trial that will examine whether ketogenic dietary intervention strategies are effective in ameliorating multiple adverse signs and symptoms in women with an incurable endocrinopathy. Thus, providing evidence suggesting this approach as a safe and effective treatment intervention in women diagnosed with PCOS.

OUTCOMES

Primary

Changes in anovulatory status in women with PCOS

Secondary

- Changes in reproductive hormones such as progesterone, estrogen, LH, FSH
- Analysis of potential predictive metabolic baseline characteristics
- Differences in blood metabolites (metabolic and lipids).

Exploratory

- Examine cardiovascular function using magnetic resonance imaging (MRI)
- Examine ovarian morphology through MRI.

PARTICIPANTS

This study aims to recruit 40 female participants between the ages of 18 to 40yr who have been diagnosed with PCOS. Each participant must meet all the inclusion criteria and none of the exclusion criteria at screening in order to participate.

Inclusion criteria:

- Female
- Ages 18 – 40 years
- Participant is willing and able to comply with all study procedures including the following prior to Test Day: fasting (>10 h; water only), no alcohol (>24 h), no exercise (>24 h), no acute illness and controlled feeding before the Test Day, maintain diet, exercise, medication, and supplement habits throughout the study.
- Participants with PCOS symptoms including oligomenorrhea-anovulation or spontaneous intermenstrual periods.
- BMI >18kg/m
- Participant understands the study procedures and signs forms providing informed consent to participate in the study.
- **Must have access to smart phone, computer or tablet to access diet.**

Exclusion criteria:

- Participant follows a low-carbohydrate diet (<30% energy from carbohydrate)
- Participant has non-PCOS etiologies of anovulation, menopause or the removal of the ovaries.
- Participant has history of type 1 diabetes
- Participant has loss of 10% bodyweight in the last 6 months
- Participant is pregnant or breast feeding
- Participant has a condition the Investigator believes would interfere with his ability to provide informed consent.

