[figure not shown]
Sample Size. In our pilot trial with a sample size of 20 participants in each intervention, we acknowledge the limitations in statistical power due to the small sample. However, for this pilot trial we plan to recruit 40 participants to investigate the effects on ovulation. The results of this pilot trial will provide initial insights, but it is essential to acknowledge the limitations imposed by the small sample size.

Recruitment:

Recruitment will occur through well-established methods at OSU which include word of mouth, ResearchMatch database, social media engagement and flyers.

METHODS

SPARK-Pilot Study Design

Study overview:

Figure 2 | Study schematic, showing timeline for a study day.

Study Procedures

Study Day	Screening	Test Day	Daily
Visit to Study Center	X	X	
Informed consent	X		
Medical intake questionnaire, diet assessment, anthropometrics ¹	X		
Body Composition Scan ²		X	
Basal Body Temperature ³			X
Urine based Ovulation predication test ⁴			X
Fingerstick Measurements ⁵			X
Hydration Status ⁶		X	
Whole blood collection ⁷		X	
Surveys ⁸		X	
Cardiovascular and Ovarian MRI ⁹		X	

1. Medical intake questionnaire and diet assessment questionnaire are attached in **Appendix**. Anthropometric data will include: Hip and Waist circumference, BMI, height and weight.
2. Lean Body Mass and fat mass assessments will be done by DXA measurement at weeks 0 and 8.
3. Participants will also be provided with an intravaginally inserted OvuCore Sensor that is designed for measuring core body temperature which rises as progesterone is

releases. Participants will insert these monitors before sleep and wear them throughout the night

4. Participants will be provided with urine ovulation predictor kit testing strips to use during the duration of the study as a tertiary predictor of potential ovulation
5. Daily fasting glucose/ketones will be assessed using capillary finger stick lancing. A small drop of blood (i.e., the size of a grain of rice) will be obtained once daily, while fasting, using enzymatic strips fitted for a handheld analyzer (KetoMojo). All the data will be stored in the device's internal memory until retrieved by the study team during test visits.
6. Prior to blood collection, participants will be asked to completely void their bladder. And hydration status will be determined via urine specific gravity (USG) reporting <1.025 . Urine will be tested for pregnancy status.

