7. Blood samples will be collected according to the schedule in Figure 2.
8. Participants will complete a menstrual history survey and Ferriman-Gallwey index survey biweekly.
9. Optional assessment of cardiovascular function using MRI at weeks 0 and 12.

Screening Visit: Participants that meet the initial qualifying criteria will visit the study center for a screening meeting. The participant and a member of the research team will meet in a private office to discuss the informed consent form. The informed consent form will be provided to the participant for their review, the study will be described in full detail and any questions the interested participant has will be encouraged and responded to. If they choose to participate in the study, they will be asked to sign the consent form providing written consent. The participant will be informed that even though they signed the consent form, their participation in the study is dependent on anthropometric measures and diet and medical questionnaire answers to determine if they meet the study criteria.

If the participant provides consent, they will be provided with questionnaires including Automated Self-administered 24-hour Dietary Assessment Tool (ASA24[®]), and medical history. All collected samples and data will be coded to maintain participant anonymity. Height and weight will be collected. If the participant is eligible for the study and is still interested in participating then they will be scheduled to return to the study center for the testing visit.

Testing Day:

Participants will report to the study center in the morning of the Test Day. Compliance with pre-test instructions (fasted $> 10h$, no alcohol $>24h$, no exercise $>24h$, consumed pre-test food) will be confirmed by the Investigator. Participants will complete a baseline menstrual history and Ferriman-Gallwey index survey. Participants will be asked to completely void their bladder and a sample will be analyzed for hydration status. Participants with samples reading greater ≥ 1.025 USG will be asked to drink 160z of water and retest again in 30 minutes. Urine will be tested for pregnancy status; a positive

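### The methods named for cycle regularity leave out baseline cycle history, which the trial already collects; with 20 women per arm this is valid but inefficient

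*Protocol*

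**What the plan says.** All the methods are in the protocol's Data Analysis and Statistical Methods section.

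- **Item 1** is descriptive: "We will provide concise summaries of menstrual cycle attributes such as cycle length, variability, and ovulation status for participants at baseline".
- **Item 2** compares time to regular cycles (21 to 35 days) by Kaplan-Meier curves and log-rank tests. It names no stratification factor or covariate.
- **Item 3** models ovulation by logistic regression and lists age, BMI and the woman's cycle characteristics at entry as potential confounders.
- **Item 4** promises hazard ratios with confidence intervals for reaching regular cycles. It does not name the model and says nothing about covariates either way.
- **Item 5** gives the participant-level test: "The proportion of participants achieving regular menstrual cycles in each diet group will be compared using appropriate statistical tests such as the chi-square test".

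The baseline information is collected. Under Testing Day: "Participants will complete a baseline menstrual history and Ferriman-Gallwey index survey". The Sample Size paragraph plans for 20 women per arm ("In our pilot trial with a sample size of 20 participants in each intervention") and says of this size: "we acknowledge the limitations in statistical power due to the small sample". The listed primary outcome is "Changes in anovulatory status in women with PCOS", not regularity, although the statistical plan opens by naming cycle regularity as what it sets out to evaluate.

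**The concern.** How irregular a woman's cycles are at entry plausibly predicts whether she reaches a 21 to 35 day pattern on study. The inclusion criteria admit women with differing cycle patterns, so this baseline will vary. Adjusting for a prognostic baseline value removes outcome variation that has nothing to do with diet. The named tests for regularity do not do this, while the ovulation model in the same section does.

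Two things are at stake. The first is power, which is already low at this size. The second is how the result reads. With 20 per arm, sizeable chance differences in baseline severity are common, and an unadjusted estimate can be explained away by one. The protocol wants these data to inform a fully powered trial, so an avoidably noisy effect estimate would carry forward.

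**Working it through.** **Inputs from the protocol.** 20 per arm, 40 in total. The protocol gives no alpha, power, event rate, effect size or prognostic strength, so there is no stated figure to reproduce.

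**Assumptions.** Two-sided alpha 0.05; no dropout; regular-cycle rates of 20% vs 50%, 20% vs 60% or 30% vs 70%; a standardised, normally distributed baseline covariate with an odds ratio (OR) of 1 to 8 per SD.

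**1. Chance imbalance.** The between-arm difference in a standardised baseline has SD √(2/20) = 0.32. A gap above 0.3 SD arises in about 34% of trials, and one above 0.5 SD in about 11%. If the log-odds slope is 1.0 per SD, a 0.5 SD gap alone is worth an odds ratio of exp(0.5) = 1.65.

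**2. Unadjusted power.** With p̄ the mean of the two rates and n = 20,

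Power = Φ{[|p₁ − p₂| − 1.96·√(2p̄(1 − p̄)/n)] / √([p₁(1 − p₁) + p₂(1 − p₂)]/n)}.

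- 20% vs 50%: (0.30 − 1.96 × 0.1508)/0.1432 = 0.03, so 51%.
- 20% vs 60%: 75%.
- 30% vs 70%: 73%.

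**3. Approximate gain.** If baseline explains a share R² of the outcome variance, the standard error shrinks by √(1 − R²). From a base power of 50%, adjusted power is Φ[1.96/√(1 − R²) − 1.96]:

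- R² 0.10: 2.066 − 1.96 = 0.106, so 54.2% (gain 4.2 points).
- R² 0.20: gain 9.1 points.
- R² 0.30: gain 14.9 points.

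For a binary outcome at these rates, OR 2 per SD corresponds to R² of about 0.07 to 0.10, OR 3 to 0.14 to 0.19, and OR 5 to 0.22 to 0.30.

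**4. Simulation, binary outcome** (3000 trials per setting, marginal rates held fixed). Power of chi-square → linear ANCOVA, in %:

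| OR per SD | 20% vs 50% | 20% vs 60% | 30% vs 70% | Gain (points) |
|---|---|---|---|---|
| 1 | 53.4 → 51.8 | 75.2 → 75.1 | 71.6 → 72.1 | −1.6 to 0.5 |
| 1.5 | 53.3 → 53.3 | 74.3 → 75.3 | 70.5 → 73.8 | 0 to 3.3 |
| 2 | 52.6 → 54.2 | 75.4 → 79.0 | 70.7 → 76.0 | 1.6 to 5.3 |
| 3 | 52.8 → 59.4 | 75.8 → 82.9 | 72.8 → 81.9 | 6.6 to 9.1 |
| 5 | 53.9 → 65.2 | 74.1 → 86.9 | 70.9 → 85.6 | 11.3 to 14.7 |
| 8 | 51.8 → 68.5 | 76.7 → 91.4 | 70.7 → 89.4 | 14.7 to 18.7 |

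A second set of runs fixed the comparator at log-odds −1 (27% regular) at average baseline, with a conditional diet odds ratio of 4.5 or 7.4. The ANCOVA gains were about 0 to 1 point with no prognosis, 3 at a log-odds slope of 0.5 per SD (OR 1.65), 7 to 9 at slope 1.0 (OR 2.7) and 12 to 16 at slope 1.5 (OR 4.5).

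**5. Type I error.** In the null runs at 30% in both arms, ANCOVA rejected in about 5%. A logistic likelihood-ratio test rejected in about 6 to 7%, so part of its apparent gain is small-sample inflation.

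**6. Simulation, time to event** (2000 trials per setting, conditional diet hazard ratio 2.5 to 3, comparator rate 20 to 30%). A covariate-adjusted Cox test beat the log-rank test by 3 to 6 points at a baseline hazard ratio of 1.5 per SD, 8 to 10 at 2, and 16 to 23 at 3. The conditional hazard ratio is held fixed here, so the log-rank power itself falls as baseline becomes more prognostic. The adjusted Cox test rejected in 5.4 to 6.4% under the null, against 4.4 to 5.8% for log-rank.

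**The case against.** The case for leaving the text alone has real weight.

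- **Validity.** Unadjusted tests remain valid under randomisation; chance imbalance is already in their error rate. Using an unadjusted test for one outcome and an adjusted regression for another is ordinary practice. A reader might infer that items 2 and 5 contradict item 3. They do not.
- **Primary outcome.** The primary outcome is anovulatory status, and its model in item 3 already considers cycle characteristics at entry. A reader might infer that the primary model lacks this covariate; the text shows otherwise.
- **Openness of the wording.** Item 5 offers chi-square only as an example. Item 4 is silent, so it cannot be called unadjusted. Covariates are often left to a statistical analysis plan.
- **Size.** The simulations assume a perfectly measured covariate with a linear effect on the log-odds, which is a best case. The content of the menstrual history survey is not shown. The entry criteria include bleeding between periods, so a simple count of bleeds need not track closeness to a regular cycle.
- **Pilot status.** The protocol concedes limited power.

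Most of this stands and limits the point. It does not remove it. The protocol itself chose methods for regularity here, and covariates for item 3. Limited power is a reason to use data already in hand, and a covariate chosen after seeing outcomes would be open to challenge.

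**Conclusion.** The point holds as a modest efficiency improvement. The methods named in items 2 and 5 do not use a baseline measure that the trial collects, summarises and already considers in item 3.

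The size rests entirely on assumed rates and prognostic strengths. Level-holding adjustment gains about 0 to 20 power points: roughly 3 to 9 for weak to moderate prognosis (log-odds slopes 0.5 to 1.0 per SD), and essentially nothing lost if baseline is not prognostic (at worst 1.6 points in these runs). A reader might infer a definite loss of, say, 12 to 17 points. The documents do not support that: it would need baseline to explain about 25 to 35% of the outcome variance, and nothing in the protocol says how much it explains.

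**What to change.** 1. **Item 5.** Make the main comparison a participant-level risk difference between arms with a 95% CI, adjusted for one prespecified baseline cycle measure. Use linear ANCOVA, or another method shown to hold its level with 40 women.
2. **Covariate.** Name it now, from the baseline menstrual history: for example, baseline cycle length or frequency. Code it so that women without periods stay in the analysis. First confirm that the survey records it.
3. **Item 4.** State that the hazard ratio comes from a Cox model with the same covariate.
4. **Items 2 and 5.** Keep the log-rank and chi-square tests as supportive.

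The cost is a few sentences, one degree of freedom and a slightly more complex analysis. No extra visit is needed, provided the survey contains the chosen measure. If a logistic model is preferred, its likelihood-ratio test should not be used without correction, since it runs at about 6% type I error at this size.
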